### 2.7.4 Diabetes assessment

Diabetes will be assessed by the analysis of:

- diabetic TEAEs
- change in glucose-related laboratory values over time
- shifts from baseline in glucose control category
- incidence of post-baseline new onset of diabetes.

Fasting glucose parameter, when used in any analysis, will require the lab sample to be taken while fasting. Glucose values recorded at non-fasting state will not be used.

#### 2.7.4.1 Diabetes TEAE

New onset/worsening of diabetes will be identified by the search criteria specified in [Appendix 5.2](#). The analysis will be performed for all subjects and then by baseline diabetes status. A subject will be identified as being diabetic at ORION-8 baseline if any of the following is true:

- The targeted medical history notes that the subject is diabetic
- The subject has ORION-8 Day 1 concomitant anti-diabetic medication (ATC level 2 code: A10)
- The ORION-8 baseline HbA1c value is  $\geq 6.5\%$
- Fasting glucose  $\geq 126$  mg/dL at ORION-8 baseline.

Baseline fasting glucose uses average of last two assessments at or prior to ORION-8 baseline.

A subject data listing will be provided for diabetic AEs. Such listing will include all AEs in ORION-8 database, regardless of whether they are ORION-8 TEAE.

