### **Medical History**

Medical history (targeted and other medical history) from the initial feeder studies (ORION-1/9/10/11) will be summarized for the Safety Population overall and by treatment group of the feeder studies. For other medical history, the sites are allowed to report in ORION-8 eCRF any relevant medical or surgical issues that occurred prior to consent in the initial feeder study but were not recorded in the feeder study, and such information added in ORION-8 eCRF should be combined with other medical history from feeder trial databases. Other medical history will be coded into Medical Dictionary for Regulatory Activities (MedDRA) terminology using the most recent MedDRA version before database lock (DBL), and will be summarized by primary system organ class (SOC) and preferred term (PT).

For targeted medical history, the following data will be summarized:

- Smoking status: Current, Former, Never, Unknown
- Hypertension: Yes, No, Unknown
- Hyperlipidemia: Yes, No, Unknown
- Congestive heart failure: Yes, No, Unknown
- Diabetes mellitus: Yes, No, Unknown
- ASCVD status: ASCVD, ASCVD risk equivalent
- Prior or current CHD (Coronary Heart Disease): Yes, No, Unknown
- Prior or current CVD (Cerebrovascular Disease): Yes, No, Unknown
- Prior or current PAD (Peripheral Artery Disease): Yes, No, Unknown
- Family history of coronary artery disease: Yes, No, Unknown
- Family history of dyslipidemia: Yes, No, Unknown

A subject is classified as ASCVD if CHD = Yes or CVD = Yes or PAD = Yes. Otherwise, the subject is ASCVD risk equivalent.

In ORION-11, the questions for CHD, CVD and PAD are asked only when the subject is indicated as ASCVD in the subject type CRF question (only ORION-11 CRF has this question). Therefore, for ORION-11 subjects who are indicated as ASCVD risk equivalent, their answers to CHD, CVD and PAD questions are all implicitly “No”.

For ORION-3 rollover subjects, CHD and CVD are derived as follows:

- CHD:
  - If prior PCI (Percutaneous Coronary Intervention) = Yes or prior MI (Myocardial Infarction) = Yes or prior CABG (Cardiovascular Arterial Bypass Graft) = Yes, then CHD = Yes.
  - Else if prior PCI = Unknown or prior MI = Unknown or prior CABG = Unknown, then CHD = Unknown.
  - Else CHD = No.
- CVD:
  - If prior stroke = Yes or prior TIA (Transient Ischaemic Attack) = Yes, then CVD = Yes.
  - Else if prior stroke = Unknown or prior TIA = Unknown, then CVD = Unknown.
  - Else CVD = No.

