#### 2.7.4.4 Incidence of post-baseline new onset of diabetes

The number of subjects who shift from no diabetes at baseline (see [Section 2.7.4.1](#) for definition of baseline diabetes) to diabetes will be summarized. A 4-component definition of diabetes will be utilized. The 4 components are provided below.

1. Diabetic TEAEs identified by the search criteria in [Appendix 5.2](#), or
2. Post-baseline fasting glucose  $\geq$ 126 mg/dL on two consecutive occasions, or
3. Initiation of anti-diabetic medication (ATC level 2 code: A10) at any time post-baseline, or
4. At least one post-baseline HbA1c  $\geq$ 6.5%.

The number of subjects who have any of the 4 components (post-baseline new-onset of diabetes) will be summarized along with each component. This analysis will be performed for those subjects who have fasting glucose at baseline < 100 mg/dL and then for those with fasting glucose at baseline  $\geq$ 100 and <126 mg/dL. Baseline fasting glucose uses average of last two assessments at or prior to ORION-8 baseline.

The time to new-onset diabetes will also be summarized. Only subjects without diabetes at baseline will be included in the analysis. The time (weeks) to new-onset diabetes will be calculated from ORION-8 Day 1.

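### The ORION-8 baseline-diabetes rule uses no feeder-trial diabetes AE or earlier feeder HbA1c, so feeder-onset cases that are untreated and below both laboratory thresholds at Day 1 can be counted as new onset.

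*SAP*

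**What the plan says.** SAP 2.7.4.1 defines baseline diabetes by four criteria joined by OR.

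- **History:** "The targeted medical history notes that the subject is diabetic".
- **Drug:** an anti-diabetic medication (ATC A10) concomitant on ORION-8 Day 1.
- **HbA1c:** "The ORION-8 baseline HbA1c value is" at least 6.5%. Under SAP 2.1.1 the laboratory baseline is the last record at or before ORION-8 baseline, which for most Phase III rollovers is the last feeder record.
- **Fasting glucose:** at least 126 mg/dL, as the mean of the last two assessments at or before ORION-8 baseline.

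On the source of the history, SAP 2.3.2 (Medical History) states: "Medical history (targeted and other medical history) from the initial feeder studies (ORION-1/9/10/11) will be summarized". Sites may add to other medical history in the ORION-8 eCRF, but only "any relevant medical or surgical issues that occurred prior to consent in the initial feeder study but were not recorded in the feeder study".

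SAP 2.7.4.4 then reports "The number of subjects who shift from no diabetes at baseline" to diabetes, taking the baseline definition from 2.7.4.1. A case needs any one of four components: a diabetic TEAE from the Appendix 5.2 search, two consecutive fasting glucose values of at least 126 mg/dL, a post-baseline A10 start, or "At least one post-baseline HbA1c" of at least 6.5%. SAP 2.7.4.1 also presents diabetes TEAEs by the same baseline status.

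**The concern.** Diabetes that began between feeder consent and ORION-8 Day 1 has no place in the history criterion. For Phase III rollovers that interval is about 18 months: Protocol Table 6-1 refers to feeder Day 540. For ORION-3 rollovers the history goes back to ORION-1, two studies earlier. If such a subject also escapes the other three criteria, the plan treats known or previously documented diabetes as absent and can later report it as arising in ORION-8.

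Diabetes mellitus is a named AE of special interest (SAP 2.7.1.1.2), and both the number of new-onset cases and the time to onset are planned outputs. There is no concurrent control in which a similar error would cancel. The same misclassification puts these subjects in the non-diabetic stratum of the 2.7.4.1 TEAE tables.

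**Working it through.** The plan gives no diabetes incidence or misclassification rate, so there is no figure to reproduce. The check is of the logic, followed by two illustrations on assumed inputs.

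**1. Who is missed.** Take a subject whose diabetes began in a feeder trial, so targeted history is No. Three yes/no criteria remain, giving 2 × 2 × 2 = 8 combinations. Seven contain at least one Yes and are classed as diabetic. One is missed: no A10 drug, HbA1c below 6.5% and mean fasting glucose below 126 mg/dL. Diet-controlled disease is an example.

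**2. How a missed subject becomes a case.**

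- *HbA1c.* It is in both the full and the limited chemistry panels (Protocol 7.1.6.3). Table 6-1 therefore schedules it at Days 90, 270, 450, 630, 810, 990 and EOS, seven times for a subject who completes. Any one value of at least 6.5% makes a case, while only the last pre-baseline value can exclude one. ORION-3 rollovers have fewer post-baseline values because their participation is shortened (SAP 1.1, 2.1).
- *A10 start.* A first prescription for diabetes already known in the feeder counts.
- *TEAE.* The diabetes search in Appendix 5.2 covers worsening as well as new onset. Under SAP 2.7.1 a worsened AE is entered as a separate record and so is a TEAE. A feeder AE that merely persists is not, unless its onset date is missing or partial and cannot be placed before baseline (SAP 5.1.2).
- *Fasting glucose.* This adds little. It is in the full panel only, scheduled only at EOS, so two consecutive post-baseline values are not scheduled.

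**3. Illustrative count.** Miscounted subjects = N × f × m × t.

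- N = 2991 enrolled (Protocol, Amendment 2 rationale).
- f = share with feeder-onset diabetes, assumed 2–8%.
- m = share of those missed by the rule, assumed 5–30%.
- t = share of the missed who later meet a component, assumed 50–100%.

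Low end: 2991 × 0.02 × 0.05 × 0.50 = 1.5. High end: 2991 × 0.08 × 0.30 × 1.00 = 71.8.

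For contrast, if the rule missed all feeder-onset diabetes (m = 100%), the range would be 2991 × 0.02 × 1 × 0.50 = 29.9 to 2991 × 0.08 × 1 × 1 = 239.3.

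**4. Asymmetry of the HbA1c rule alone.** I simulated 400,000 subjects per scenario with no true change in HbA1c. All inputs are assumed: no history or drug, mean 5.7–5.8%, between-subject SD 0.35–0.40, within-subject SD 0.15–0.25, three to five feeder values with the last as baseline, seven ORION-8 values, rounding to 0.1%.

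- Among subjects classed as non-diabetic, 2–13% had an earlier feeder value of at least 6.5%.
- They made up 28–54% of the HbA1c-component cases.
- Adding true incident cases equal to 3–10% of the at-risk set lowered that share to 10–43%.
- Only about 6–19% of these repeat crossers had a true mean of at least 6.5%.

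**The case against.** A reader might infer that the rule ignores feeder-onset diabetes altogether, so that prevalent cases in general are counted as new. The documents do not support that: three of the four criteria are assessed at ORION-8 baseline, and they capture disease that is treated or still in the diabetic range.

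A reader might also take the simulated 28–54% as the share of reported cases that are really feeder-onset diabetes. That does not follow either. The figure sets true incidence to zero, leaves out the glucose and A10 criteria, and rests on inputs the documents do not give. Most of the repeat crossers (81–94%) have a true mean below 6.5%, and measurement variation took them over the threshold both before and after baseline.

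Three further points stand in part.

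- **Resetting baseline at ORION-8 Day 1 is coherent.** It matches the TEAE and laboratory baselines used elsewhere in the SAP. But it does not make a diagnosis recorded before that date a new onset after it.
- **Other displays help.** The diabetic-AE listing covers all AEs in the ORION-8 database, ongoing feeder AEs are followed (Protocol Table 6-1, footnote 12), and each component is shown separately. A reader could trace some cases, but the summary count would not be corrected.
- **Over-counting errs on the cautious side for safety, and excluding everyone with a single feeder HbA1c of at least 6.5% would remove the borderline subjects at highest risk.** This is a good reason to keep the HbA1c exclusion out of the main analysis. It does not apply to a recorded diagnosis.

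**Conclusion.** The point holds for one defined group: feeder-onset cases with no A10 drug and with HbA1c and mean fasting glucose both below threshold at ORION-8 baseline. These subjects can be counted as new onset in SAP 2.7.4.4 and are placed in the non-diabetic stratum in 2.7.4.1.

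The direction is certain for the number of new-onset cases, since wrongly admitting subjects to the at-risk set cannot remove a case. The percentage also rises if these subjects meet a component more often than the rest of the at-risk set, which is likely but not shown by the documents.

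The size is unknown. The range of about 1.5 to 72 of 2991 rests wholly on assumed rates. The outputs affected are descriptive safety displays; the primary efficacy endpoint is untouched. The change is worth making because it is cheap and removes a one-directional error from an AE of special interest.

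**What to change.** 1. Add a fifth criterion to the baseline list in SAP 2.7.4.1: a diabetes-diagnosis AE recorded in ORION-1, 3, 9, 10 or 11 with onset before ORION-8 baseline. List the qualifying preferred terms, because the Appendix 5.2 search also takes in worsening and glucose-test terms.
2. Use the revised status in both 2.7.4.1 and 2.7.4.4.
3. Add a sensitivity display of 2.7.4.4 that also excludes subjects with any feeder HbA1c of at least 6.5% before ORION-8 baseline. Keep this out of the main analysis, for the reason given under the objection.

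The cost is SAP wording, one derivation from feeder data the sponsor should already hold, and one further table. No new data are collected. The at-risk set becomes somewhat smaller, and the reduction should be reported in both displays. Under the simulation's assumptions the HbA1c exclusion alone would remove 2–13% of subjects otherwise classed as non-diabetic.

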#### 2.7.4.2 Change in glucose-related laboratory values over time

This analysis only utilizes laboratory data (fasting glucose and HbA1c). The change from baseline to EOS will be summarized for fasting glucose for all subjects and then by baseline glucose control status. The change from baseline to the EOS and to the worst observation will be summarized for HbA1c for all subjects and then by baseline glucose control status. Baseline glucose control status will be identified separately for fasting glucose and HbA1c using the values provided in the table below (note that medical history will not be taken into account for this analysis). Figures will also be created showing mean HbA1c values over time by baseline glucose control status.

Parameter	Baseline Glucose Control Status	Baseline Laboratory Values
Fasting Glucose*	Normal	<100 mg/dL
	Impaired	$\geq 100$ to <126 mg/dL
	Diabetes	$\geq 126$ mg/dL
HbA1c	Normal	<5.7%
	Impaired	$\geq 5.7$ to <6.5%
	Diabetes	$\geq 6.5\%$

\* Baseline uses average of last two fasting glucose assessments at or prior to ORION-8 baseline.

### 2.7.4.3 Shifts from baseline in glucose control category

Shifts from baseline in glucose control category will be summarized in two different ways: the change from ORION-8 baseline to the worst and then again for the change to last glucose control category. Note that medical history will not be taken into account for this analysis. If consecutive fasting glucose measurements fall in two separate categories, or if only one pre- or post-baseline fasting glucose measurement is available, then the classification will be based on the HbA1c measurements only. If HbA1c is missing, then both consecutive fasting glucose measurements must fall in a category otherwise the lower category will be used.

Shift Category*	Baseline Values*	Post-baseline Values
Normal to Normal (no change)	Fasting glucose < 100 mg/dL on the last two measurements at or prior to ORION-8 baseline AND HbA1c < 5.7%	Fasting glucose < 100 mg/dL on two consecutive occasions AND HbA1c < 5.7%
Normal to Impaired	Fasting glucose < 100 mg/dL on the last two measurements at or prior to ORION-8 baseline AND HbA1c < 5.7%	Fasting glucose ≥ 100 and < 126 mg/dL on two consecutive occasions OR HbA1c ≥ 5.7 and < 6.5%
Normal to Diabetes	Fasting glucose < 100 mg/dL on the last two measurements at or prior to ORION-8 baseline AND HbA1c < 5.7%	Fasting glucose ≥ 126 mg/dL on two consecutive occasions OR HbA1c ≥ 6.5%
Impaired to Normal	Fasting glucose ≥ 100 and < 126 mg/dL on the last two measurements at or prior to ORION-8 baseline OR HbA1c ≥ 5.7 and < 6.5%	Fasting glucose < 100 mg/dL on two consecutive occasions AND HbA1c < 5.7%
Impaired to Impaired (no change)	Fasting glucose ≥ 100 and < 126 mg/dL on the last two measurements at or prior to ORION-8 baseline OR HbA1c ≥ 5.7 and < 6.5%	Fasting glucose ≥ 100 and < 126 mg/dL on two consecutive occasions OR HbA1c ≥ 5.7 and < 6.5%
Impaired to Diabetes	Fasting glucose ≥ 100 and < 126 mg/dL on the last two measurements at or prior to ORION-8 baseline OR HbA1c ≥ 5.7 and < 6.5%	Fasting glucose ≥ 126 mg/dL on two consecutive occasions OR HbA1c ≥ 6.5%
Diabetes to Normal	Fasting glucose ≥ 126 mg/dL on the last two measurements at or prior to ORION-8 baseline	Fasting glucose < 100 mg/dL on two consecutive occasions AND

	OR HbA1c $\geq$ 6.5%	HbA1c < 5.7%
Diabetes to Impaired	Fasting glucose $\geq$ 126 mg/dL on the last two measurements at or prior to ORION-8 baseline OR HbA1c $\geq$ 6.5%	Fasting glucose $\geq$ 100 and < 126 mg/dL on two consecutive occasions OR HbA1c $\geq$ 5.7 and < 6.5%
Diabetes to Diabetes (no change)	Fasting glucose $\geq$ 126 mg/dL on the last two measurements at or prior to ORION-8 baseline OR HbA1c $\geq$ 6.5%	Fasting glucose $\geq$ 126 mg/dL on two consecutive occasions OR HbA1c $\geq$ 6.5%

\*No change (Normal to Normal, Impaired to Impaired, and Diabetes to Diabetes), Worsened (Normal to Impaired, Normal to Diabetes, and Impaired to Diabetes), and Improved (Impaired to Normal, Diabetes to Impaired, and Diabetes to Normal) categories will also be summarized.

Diabetes takes precedence over impaired, i.e. if a subject satisfies the diabetes criteria, the subject cannot be in impaired category.

#### 2.7.4.4 Incidence of post-baseline new onset of diabetes

The number of subjects who shift from no diabetes at baseline (see [Section 2.7.4.1](#) for definition of baseline diabetes) to diabetes will be summarized. A 4-component definition of diabetes will be utilized. The 4 components are provided below.

1. Diabetic TEAEs identified by the search criteria in [Appendix 5.2](#), or
2. Post-baseline fasting glucose  $\geq$ 126 mg/dL on two consecutive occasions, or
3. Initiation of anti-diabetic medication (ATC level 2 code: A10) at any time post-baseline, or
4. At least one post-baseline HbA1c  $\geq$ 6.5%.

The number of subjects who have any of the 4 components (post-baseline new-onset of diabetes) will be summarized along with each component. This analysis will be performed for those subjects who have fasting glucose at baseline < 100 mg/dL and then for those with fasting glucose at baseline  $\geq$ 100 and <126 mg/dL. Baseline fasting glucose uses average of last two assessments at or prior to ORION-8 baseline.

The time to new-onset diabetes will also be summarized. Only subjects without diabetes at baseline will be included in the analysis. The time (weeks) to new-onset diabetes will be calculated from ORION-8 Day 1.

#### 2.7.5 Other safety data

##### 2.7.5.1 ECG and cardiac imaging data

Not applicable to this study.

### 2.7.5.2 Vital signs

Observed value, change, and percent change from ORION-8 baseline in vital signs (blood pressure and heart rate) will be summarized descriptively at ORION-8 baseline (for observed value only) and at each scheduled time point from Day 90 to Day 1080 and at EOS.

The change from ORION-8 baseline to EOS will also be summarized by the following categories:

- Systolic blood pressure (mmHg):
  - $\leq -20$
  - $> -20$  to  $\leq -10$
  - $> -10$  to  $\leq -5$
  - $> -5$  to  $< 5$
  - $\geq 5$  to  $< 10$
  - $\geq 10$  to  $< 20$
  - $\geq 20$
- Diastolic blood pressure (mmHg):
  - $\leq -10$
  - $> -10$  to  $\leq -5$
  - $> -5$  to  $\leq -3$
  - $> -3$  to  $< 3$
  - $\geq 3$  to  $< 5$
  - $\geq 5$  to  $< 10$
  - $\geq 10$

### 2.8 Pharmacokinetic endpoints

Not applicable to this study.

### 2.9 PD and PK/PD analyses

Not applicable to this study.

## **2.10 Subject-reported outcomes**

Not applicable to this study.

## **2.11 Biomarkers**

Not applicable to this study.

## **2.12 Other Exploratory analyses**

No exploratory analyses are planned for this study.

## **2.13 Interim analysis**

No formal interim analysis will be performed in this study.

## **3 Sample size calculation**

This study will be a long-term extension study of ORION-3/9/10/11 and all completers of those studies who fulfill ORION-8 entry criteria and willing to participate can be enrolled into this study.

## **4 Change to protocol specified analyses**

No change from protocol specified analysis was made.

## **5 Appendix**

### **5.1 Imputation rules**

#### **5.1.1 Study drug**

Missing/partial start date or end date of treatment will not be imputed.

#### **5.1.2 AE date imputation**

An AE with an unknown or partial onset date will be categorized as a TEAE unless there is sufficient information to determine that the event began before baseline. For example, if an AE's resolution date/time < baseline date/time, the AE's onset date/time is logically < baseline date/time and thus it is not a TEAE.

#### **5.1.3 Concomitant medication date imputation**

Any medication with both start and stop dates missing are considered as baseline concomitant medication. Any medication with only start date missing are considered as either prior or baseline concomitant medication depending on the stop date. Any medication with only stop date missing are considered as either baseline concomitant or new/changed concomitant medications depending on the start date.

## 5.2 Standardized MedDRA queries (SMQ) and AE terms for additional AE investigations

1. Hepatic events
  - Drug related hepatic disorders - comprehensive search (SMQ, broad and narrow)
2. Renal events
  - Acute renal failure (SMQ, broad and narrow)
3. Hypersensitivity
  - Hypersensitivity' (SMQ, broad and narrow) excluding
    - PTs 'infusion site %' ('infusion site dermatitis', 'infusion site eczema', 'infusion site hypersensitivity', 'infusion site rash', 'infusion site urticaria', 'infusion site vasculitis) and
    - PTs 'injection site %' ('injection site dermatitis', 'injection site eczema', 'injection site hypersensitivity', 'injection site rash', 'injection site urticaria' and 'injection site vasculitis')
4. Neurological events and neurocognitive disorders
  - Neurological events
    - Demyelination, (SMQ, broad and narrow)
    - Peripheral neuropathy, (SMQ, broad and narrow)
  - Neurocognitive disorders
    - Deliria (incl confusion), (HLGT)
    - Cognitive and attention disorders and disturbances, (HLGT)
    - Dementia and amnesic conditions, (HLGT)
    - Disturbances in thinking and perception (HLGT)
    - Mental impairment disorders (HLGT)
5. Ophthalmologic events
  - Optic nerve disorders, (SMQ, broad and narrow)
  - Retinal disorders, (SMQ, narrow)
  - Corneal disorders, (SMQ, narrow)
6. Cardiac safety: Major adverse cardiovascular events (MACE)
  - CV death
    - Fatal SAEs in Cardiac disorders SOC
    - Fatal SAEs in General disorders and administration site conditions SOC: PTs 'Death', 'Sudden cardiac death', 'Cardiac death', 'Apparent death'

- Central nervous system haemorrhages and cerebrovascular accidents (HLT), fatal events only
  - Resuscitated cardiac arrest
    - Non-fatal AEs with PT ‘Cardiac arrest’
  - Non-fatal MI
    - Myocardial infarction (SMQ, broad and narrow), nonfatal events only
  - Non-fatal stroke
    - Central Nervous System hemorrhages and cerebrovascular accidents (HLT), non-fatal events only
7. New onset/worsening of diabetes
- Hyperglycaemia/new onset diabetes mellitus (SMQ, narrow)
  - Diabetic complications (HLGT)
  - Diabetes Mellitus (incl subtypes) (HLT)
  - Carbohydrate tolerance analyses (incl diabetes) HLT, excluding PT “Blood glucose decreased”

